3.6. Subject Exclusion Criteria

Subjects with any of the following criteria should be excluded:

- 1. Pregnant or lactating females.
- 2. Co-existing clinically significant aneurismal disease of the abdominal aorta, iliac or popliteal arteries.
- 3. Significant gastrointestinal bleeding or any coagulopathy that would contraindicate the use of anti-platelet therapy.
- 4. Known intolerance to study medications, everolimus or contrast agents.
- 5. Doubts in the willingness or capability of the subject to allow follow-up examinations.
- 6. Subject is actively participating in another investigational device or drug study.
- 7. History of hemorrhagic stroke within 3 months prior to treatment
- 8. Previous or planned surgical or interventional procedure within 30 days of index procedure.
- 9. Prior vascular surgery of the target lesion.
- 10. Lesion length is <3 cm or >15 cm or there is no normal proximal arterial segment in which duplex ultrasound velocity ratios can be measured.
- 11. Known inadequate distal outflow.
- 12. Significant inflow disease.
- 13. Acute or sub-acute thrombus in target vessel.
- 14. Use of adjunctive therapies (i.e. laser, atherectomy, cryoplasty, scoring/cutting balloons, brachytherapy, lithotripsy).
- 15. Outflow arteries (distal popliteal, anterior or posterior tibial or peroneal arteries) with significant lesions (≥ 50% stenosis) may not be treated during the same procedure.
- 16. Treatment of the contralateral limb during the same procedure or within 30 days of the study procedure.
- 17. Rutherford classification of 0, 1, 5 or 6.
- 18. Presence of prohibitive calcification that precludes adequate PTA treatment.
- 19. Subjects held in custody in an institution by official or court order.

3.7. Subject Enrollment Point

All subjects who are candidates for endovascular treatment of the SFA or popliteal artery will undergo screening for study eligibility and, if applicable, for study

Confidential Page 18 of 79

enrollment. For any subject enrolled, a signature of informed consent will be obtained. The subject will be considered enrolled into the study upon the completion of all the following:

- A signed subject informed consent.
- Angiographic criteria for enrollment have been met.
- Successful treatment of the inflow (iliac) artery without complication, if applicable.
- Target lesion is successfully crossed by a guidewire.
- CVT Everolimus-coated PTA Catheter has entered the vasculature.

3.8. Subject Discontinuation

Every subject should remain in the study until completion of the required follow-up period; however, a subject's participation in any clinical trial is voluntary and the subject has the right to withdraw at any time without penalty or loss of benefit. The reason for withdrawal, when it occurs, must be documented in the subject's medical record. Following study discontinuation, the subject will be followed per the institution's standard of care. Conceivable reasons for discontinuation may include, but are not limited to, the following:

- Subject participation in a clinical trial is voluntary and the subject may discontinue participation (refuse all subsequent testing/follow-up) at any time.
- Investigator may terminate the subject's participation without regard to the subject's consent if the Investigator believes discontinuation in the study is medically necessary.
- Subject does not complete the scheduled follow-up but has not 'officially' withdrawn from the trial (e.g. "lost to follow-up"). This does not apply to missed visits.
- Medical conditions such as the following:
 - Reaction to acute treatment that requires alternative treatment or intervention (e.g. allergic reaction to everolimus, complication with non-study device) where study objectives cannot be objectively evaluated.
 - Unanticipated hospitalization requiring treatment or therapy conflictive with study objectives and preventing compliance with study requirements.

Site personnel should make all reasonable efforts to locate and communicate with subjects at each contact time point. A minimum of two (2) telephone calls to contact the subject should be recorded in the source documents, including date, time, and initials of site personnel trying to make contact. If these attempts are unsuccessful, a letter should be sent to the subject. If the subject misses two (2) consecutive scheduled contact time points and the above mentioned attempts at communicating with the subject are attempted but unsuccessful, the subject will be considered "lost to follow-up".

Confidential Page 19 of 79

A study completion form must be completed when a) the subject is considered "lost to follow-up" (per the above criteria), b) the subject withdraws from the study or c) the investigator withdraws the subject from the study. In each case of subject discontinuation, CVT must be notified of the reason for subject discontinuation. The site will provide this information on the case report form (CRF) and in source documents.

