5. ADVERSE EVENTS

5.1. Adverse Events

At each evaluation, the investigator will determine whether any adverse events (AEs) have occurred. For the purpose of this protocol, an adverse event is any untoward medical occurrence, unintended disease or injury or untoward clinical signs (including laboratory findings) in subjects, users or other persons, whether or not related to the investigational medical device.

In this study, subjects should be encouraged to report AEs spontaneously or in response to general, non-directed questioning. If it is determined that an AE has occurred, the investigator should obtain all the information required to complete the AE Form of the CRF.

In addition, subjects will be instructed to contact the investigator, and/or study coordinator if any significant adverse events (e.g., MAE) occur between study evaluation visits.

Adverse event reporting begins when the index procedure is completed.

Adverse events should be followed to resolution or stabilization, and if an ongoing AE changes in severity, a new AE entry for this event should be recorded. If a mild adverse event changes to a moderate or severe adverse event, the end date for the mild event and the start date for the moderate or severe event should be the same. Additionally, the mild event is considered resolved with the initiation of the moderate or severe event.

Adverse events that are present at the end of a subject's participation in the study should be marked as on-going on the case report form and the subject should receive post-treatment follow-up as appropriate.

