6.4. Statistical Analyses

Detailed analyses of the primary endpoints will be performed when all of the subjects complete their primary follow-up visit at 180 days. No effort will be made to impute or extrapolate data to replace missing values. All calculations will be based on available data with missing data excluded. Any unused or spurious data will be noted as

Confidential Page 36 of 79

appropriate in the final report.

Analysis of Primary Endpoints

The primary effectiveness endpoint of patency at six (6) months will be analyzed on a per-subject basis for the evaluable populations.

The primary safety endpoint of freedom from MAE at 6 months will be analyzed using the safety population.

For both primary endpoints (ffMAE and patency at 6 months), percentages and exact 95% confidence intervals using Clopper-Pearson's method will be calculated.

Analysis of Secondary Endpoints

All secondary endpoints will be analyzed for the per-treatment evaluable population descriptive statistics will be provided to gain better understanding of the data.

For binary variables such as MAE or technical success counts, percentages, and exact 95% confidence intervals using Clopper-Pearson's method will be calculated. For continuous variables, means, standard deviations, and 95% confidence intervals for the mean using the Gaussian approximation will be calculated. If the assumption of normality seems untenable, nonparametric summary statistics will be presented instead.

For time-to-event variables, such as time to target lesion revascularization, survival curves will be constructed using Kaplan-Meier estimates, and log rank test results will be displayed for descriptive purposes only.

Analysis of Other Data

The clinical laboratory values collected will be analyzed by tabulating the number and percentage of subjects with clinically significant changes from baseline for each parameter at each time point.

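### Section 3.8 lets a subject leave the study on medical grounds with no provision for later MAE or vital-status contact, so losses from the safety estimates may be informative

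*Combined protocol and SAP*

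**What the plan says.** Section 3.8 opens with a retention statement: "Every subject should remain in the study until completion of the required follow-up period". It then gives conceivable reasons for discontinuation. Three matter here.

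- A treatment reaction: "Reaction to acute treatment that requires alternative treatment or intervention (e.g. allergic reaction to everolimus, complication with non-study device"). A limiting condition is attached: the reason applies only if it is no longer possible to judge the objectives of the study objectively.
- A hospitalization, with two joint conditions: "Unanticipated hospitalization requiring treatment or therapy conflictive with study objectives and preventing compliance with study requirements".
- The investigator's judgement: "Investigator may terminate the subject's participation without regard to the subject's consent if the Investigator believes discontinuation in the study is medically necessary".

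What happens next is one sentence: "Following study discontinuation, the subject will be followed per the institution's standard of care". The closing paragraph of 3.8 requires a study completion form, including when the investigator withdraws the subject (item c), and the reason goes to the sponsor.

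Section 5.1 says "Adverse events should be followed to resolution or stabilization". It also lets events still open when participation ends be marked as ongoing, with further care as appropriate. Section 6.2 keeps every enrolled subject whose procedure was started in the safety population. Section 6.4 rules out imputation and adds "All calculations will be based on available data with missing data excluded".

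**The concern.** In a drug trial with repeated dosing, discontinuation may mean stopping treatment while follow-up goes on. Here the balloon is used in a single index procedure and nothing remains to be stopped. Discontinuation under 3.8 can therefore only mean the end of study follow-up, and the section does not separate the two.

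The conditions attached to the medical reasons do not close the gap. They refer to the study objectives as a whole, which cover both safety and restenosis. A subject who needs alternative treatment may become unevaluable for patency while all three MAE components can still be established. Whether the objectives can still be judged is left to the site.

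If subjects leave because something went wrong, their later MAE risk may differ from that of subjects who stay. Any such loss would affect the primary 6-month safety estimate and the secondary MAE rates at 1, 2 and 3 years. Section 9.6 calls this a first-in-human study, so the later course of subjects with a drug reaction is itself information the trial is meant to yield.

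**Working it through.** **Can a later MAE go unrecorded under the plan as written?**

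1. A subject is discontinued under one of the three reasons in 3.8 before any MAE.
2. Section 3.8 hands the subject to standard of care. Neither 3.8 nor 4.6 nor Table 2 provides a study contact after discontinuation.
3. Section 5.1 asks that the known event be followed. It does not ask about a new MAE months later.
4. The subject stays in the safety population (6.2) but has no 6-month MAE status, and 6.4 excludes missing data. The subject drops out of numerator and denominator.

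So the plan permits it. The contacts that would prevent it already exist: 30 days (phone or visit), 6 and 12 months (visits), 24 and 36 months (phone calls), all with adverse event collection in Table 2.

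**The plan's own figures (section 6.3).** Inputs: N = 75, safety OPC 70%, assumed rate 70% + 15 points = 85%, one-sided alpha 0.025. Method: exact binomial, with Clopper-Pearson limits as in 6.4.

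- The smallest count whose lower 95% limit exceeds 70% is 61 of 75. P(X ≥ 61 | 75, 0.70) = 1.9%. P(X ≥ 61 | 75, 0.85) = 85.3%, against the stated 85%.
- For 64/75 the interval is 75.3% to 92.4%, as printed in the plan.

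**Sensitivity: type I error.** Assumptions, since the documents give no rate of medical discontinuation: the true 6-month freedom from MAE equals the OPC of 70%; each subject who would have an MAE is independently lost before it with probability q and excluded; no event-free subject is lost. Expected MAEs are 75 × 0.30 = 22.5. The apparent rate is about 0.70 / [0.70 + 0.30(1 − q)]. Type I error is the probability, summed over all outcomes, that the Clopper-Pearson lower limit on the remaining subjects exceeds 70%.

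| q | MAE subjects lost (22.5 × q) | Apparent rate | One-sided type I error |
|---|---|---|---|
| 0 | 0 | 70.0% | 1.9% |
| 5% | 1.1 | 71.1% | 2.9% |
| 10% | 2.25 | 72.2% | 4.2% |
| 20% | 4.5 | 74.5% | 9.5% |

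**Sensitivity: single results near the boundary.** The event-free count is fixed, and subjects who would have had an MAE are removed from the denominator.

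| Result | Rate | Lower 95% limit | Above 70%? |
|---|---|---|---|
| 60/75 | 80.0% | 69.2% | no |
| 60/74 | 81.1% | 70.3% | yes |
| 60/73 | 82.2% | 71.5% | yes |
| 59/75 | 78.7% | 67.7% | no |
| 59/74 | 79.7% | 68.8% | no |
| 59/73 | 80.8% | 69.9% | no |

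One lost subject changes the reading at 60/75. With 59 event-free subjects, even two lost do not.

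**The case against.** The other side has real points, and several stand.

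- A reader might infer that any reaction, procedural complication or hospitalization takes a subject out of the study. The text does not say that. The reasons are only conceivable ones under a general retention statement, both medical reasons are conditional, and the complication named is one with a non-study device. Only the everolimus example is harm from the study device, and the hospitalization need not be device-related.
- A reader might infer that 3.8 contradicts 5.1. It does not. Known events can be marked ongoing at exit and cared for as appropriate, so a site can comply with both. The two sections are in tension, no more.
- An allergic reaction or a hospitalization is not an MAE component. It is recorded as an adverse event when it occurs, and an MAE before exit still counts.
- That such subjects carry a higher later MAE risk is plausible, but the documents do not show it. The direction of bias in the tables follows from the assumption made.
- Sections 6.1 and 6.3 say that reaching significance does not settle whether the device deserves further study, so crossing 70% is not a binding decision rule.

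The last point does not remove the concern. Those sections put the weight on estimating the event rate and its interval, which is what selective loss would distort. It is also true that the exclusion comes from 6.4 and applies to every dropout. Section 3.8 adds avoidable dropouts whose reason for leaving may be related to outcome.

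**Conclusion.** The point holds in a limited form. Section 3.8 permits, but does not require, the end of safety follow-up on medical grounds after a single-application device. No section provides for MAE or vital-status contact afterwards, and 6.4 then excludes the subject. Possibly informative loss can bias freedom from MAE at 6 months and MAE at 1, 2 and 3 years.

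The size cannot be fixed from the documents. If 5% to 20% of subjects with an MAE were lost this way, and no event-free subjects were, one-sided type I error at a true rate of 70% would be 2.9% to 9.5% instead of 1.9%. These are sensitivity figures, not predictions.

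A reader might conclude from 60/75 becoming 60/74 that a single lost subject generally decides the safety result. That is a boundary case. At the planned rate of 85%, exactly 60 of 75 has a probability of about 5.8%, and one event-free subject fewer removes the effect.

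**What to change.** Amend 3.8, and align item (c) of its closing paragraph, so that the listed medical conditions and investigator discontinuation end only the assessments that can no longer be done, such as duplex ultrasound or the walking test. Record those as missed assessments. Adverse event, MAE and vital-status contacts continue on the existing schedule to 36 months unless the subject withdraws consent or is lost to follow-up.

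Keep the investigator's medical-necessity provision. It can stand once it no longer ends outcome contact, so deleting it is unnecessary. When a subject withdraws, ask whether the 24- and 36-month calls or a vital-status check are still permitted.

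The cost is amendment wording, site training and a few contacts that are already scheduled. No new procedure is needed. Outcomes lost after an exit may not be recoverable later.

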3.9. Early Termination of the Clinical Study

CVT, the trial sponsor, reserves the right to discontinue the clinical study at any stage, with suitable written notice to the investigator. The investigator may also discontinue participation in the clinical trial with suitable written notice to CVT.

CVT and the Study Steering Committee will monitor the progression of the study. The study will be suspended or discontinued early if there is an observation of serious adverse reactions presenting an unreasonable risk to the study population. Per definition, this would be the case in the event that the Major Adverse Event (MAE) rate reaches a level greater that the upper limit of the 95% confidence interval of the anticipated MAE. MAE is defined as a composite rate of cardiovascular death, index limb amputation and ischemia-driven target lesion revascularization (TLR).

Notification of study suspension or termination will occur no later than five (5) working days after the sponsor makes the determination. In the event of study suspension or termination, the sponsor will send a report outlining the circumstances to the IRB/EC and all investigators. A suspended or terminated study may not be re-initiated without approval of the reviewing IRB/EC (where applicable).

4. CONDUCT OF THE STUDY

Study conduct as well as detail of pre-procedure, procedural, discharge and follow up activities are presented in this section of the protocol. Refer to **Table 2** for a summary of pre-procedure, procedure, discharge and follow up activities.

4.1. Baseline Assessments

Subject preparation will occur in accordance with standard hospital policy for the care of interventional endovascular subjects. Baseline assessments will be documented in the subject medical record and on the case report form (CRF) as appropriate.

Subject History

Subject history will include, but not be limited to, the following risk factors and comorbidities: age, height, weight, body mass index (BMI), gender, hypertension, hyperlipidemia, diabetes mellitus, smoking, ischemic heart disease (history of myocardial infarction, angina pectoris, previous percutaneous or surgical coronary revascularization), history of peripheral vascular disease (previous percutaneous or surgical revascularization), deep vein thrombosis, congestive heart failure, renal insufficiency, renal disease, liver disease, cerebrovascular disease (known carotid artery disease, history of minor or major stroke or transient ischemic attack), and chronic obstructive pulmonary disease (COPD).

Medication History

A medication history should be documented which includes chronic concomitant

Confidential Page 20 of 79

medications and protocol-required medications.

Clinical Assessments

The dorsalis pedis and posterior tibial pulses for the treated limb should be documented. The distal ipsilateral extremity should be examined to ensure no gangrene or ischemic ulcers are present.

Hemodynamic Evaluation

Ankle brachial index (ABI) measurement will be obtained for the target limb.

Functional Status

Functional status using the Rutherford Becker Clinical Categories will be determined for the target limb.

Subject-perceived walking performance will be evaluated utilizing a walking impairment questionnaire (WIQ).

Walking distance will be evaluated using either the Walking Test or the Treadmill Test.

Claudication at rest and after walking will be noted.

Laboratory Assessments

A pregnancy test should be administered to all female subjects of childbearing potential within 14 days of the procedure.

The following laboratory tests should be obtained for all subjects within 7 days of the index procedure.

- Hemoglobin
- Hematocrit
- White Blood Cell Count
- Absolute Platelet Count
- Serum Creatinine
- Coagulation tests as per standard of care of the hospital (e.g., Prothrombin Time (PT) and activated Prothrombin Time (aPTT).

Duplex Ultrasonography Assessment (Optional)

At the discretion of the investigator, duplex ultrasonography may be performed according to the ultrasound core laboratory guidelines.

4.2. Concomitant Medical Therapy

Prior to the study procedure, it is required that subjects receive aspirin (ASA) and either clopidogrel or ticlopidine (only if subject has known allergy to clopidogrel or prasugrel) per hospital standard of care (either antiplatelet medication 3 days pre-procedure or loading dose on the day of intervention). Recommended aspirin dose is 100 mg daily; for clopidogrel the recommended dose is 75 mg daily and for ticlopidine 250 mg twice a day.

Confidential Page 21 of 79

4.3. SFA PTA Procedure

Procedural Medications

During the procedure, subjects will receive appropriate anticoagulation and other therapy according to standard hospital practice. The use of any medication for the treatment of vessel spasm, subject agitation or discomfort, hypotension, arrhythmias and hemodynamic changes during the procedure is at the discretion of the investigator.

Baseline Angiography

The diagnostic and interventional procedure can be conducted via either contralateral or antegrade approach at the investigator's discretion. A pelvic angiogram (digital subtraction angiography, Magnetic Resonance (MR) angiography, or Computed Tomography (CT) angiography) with run-off must have been performed prior to the PTA procedure (run-off should include popliteal and distal vessels) to confirm patent inflow and outflow as well as run-off required within the inclusion criteria.

Treatment Strategy

This study allows for treatment of *de novo* occluded/stenotic or re-occluded/restenotic superficial femoral (SFA) or popliteal artery (P1 segment) lesions in a single limb that are \geq 3 cm (30 mm) and \leq 15 cm (150 mm) in cumulative length, with up to two (2) CVT Everolimus-coated PTA Catheters. The lesion(s) should be within 1 cm distal to the femoral bifurcation in the SFA and 3 cm from the proximal margin of the intercondylar fossa.

The timing and method of treatment of any contralateral non-target lesion(s) is at the discretion of the investigator; however, it should be >30 days before or after the study procedure. A contralateral non-target lesion(s) cannot be treated during the same procedure in order to avoid complications.

Subjects selected for treatment must have a patent inflow artery and outflow arteries free from significant lesions (\geq 50% stenosis) as confirmed by angiography. If the ipsilateral iliac artery is diseased, but not occluded, it may be treated prior to the treatment of the target SFA/popliteal lesion. Successful treatment of the inflow artery is defined as attainment of final residual diameter stenosis of <30% without residual dissection or complication during the treatment. Outflow arteries (distal popliteal, anterior or posterior tibial or peroneal arteries) with significant lesions (\geq 50% stenosis) may not be treated during the same procedure.

Pre-dilatation will be performed for all target lesions with a non-study balloon catheter. After pre-dilatation, the investigator will determine the suitability of the lesion for treatment by PTA alone.

The target lesion should be treated after meeting the general and angiographic inclusion and exclusion criteria. Additional treatment modalities, including but not limited to, rotational or directional atherectomy, cryoplasty, scoring/cutting balloons, laser, brachytherapy or lithotripsy must not be performed in conjunction with this procedure.

The balloons should be sized to ensure the full length of the lesion is treated and that the balloon, upon inflation, apposes the arterial wall without oversizing.

Confidential Page 22 of 79

The initial inflation of the study device should be ≥ 1 minute.

For a residual stenosis >50% or significant dissection after study treatment, post-dilatation should be performed. A commercially available non-drug eluting nitinol stent may be used to treat a flow-limiting dissection or persistent residual stenosis if balloon inflation is unsuccessful. Post-dilatation of the stent, if required, should be done with the CVT Everolimus-coated PTA Catheter.

PTA Procedure

The appropriate balloon size will be selected after review of the subject's baseline angiogram and determination of the reference vessel diameter and lesion length.

Pre-dilatation will be performed on all subjects per the following sequence: after crossing of the target lesion with a guidewire, pre-dilatation will be performed with a non-study balloon catheter. Based on the suitability of the lesion, the investigator will determine if the lesion can be treated by PTA alone or if treatment with a stent is required (e.g. dissection, stenosis >50%). If a stent is required, the investigator will implant the stent and the patient cannot be included in the study (e.g. screen fail). If the lesion is suitable for PTA treatment alone, the CVT Everolimus- coated PTA Catheter will be used to treat the lesion.

All catheters, including the CVT Everolimus-coated PTA Catheter, should be delivered and deployed per their respective Instructions for Use (reference Appendix E for CVT Everolimus-coated PTA Catheter IFU). All balloon inflations and stent deployments, when applicable, should be captured per the angiographic core laboratory guidelines.

Criteria for Bail-Out or Alternative Procedures

For a post-treatment residual stenosis >50% or significant dissection after study treatment, post-dilatation should be performed. A commercially available nitinol stent may be used to treat a flow-limiting dissection or persistent residual stenosis >50% only after post-dilatation inflation is unsuccessful. If stent post-dilatation is performed, a CVT Everolimus-coated PTA Catheter should be used.

Angiography following PTA

Angiographic imaging is to be performed according to the angiographic core laboratory protocol and will include runoff into the distal extremity. Post-procedural images should be captured in a precise manner such as was used for the pre-procedure images.

